3 STUDY POPULATIONS

3.1 Recruitment Procedures

This study will enroll 400 adult non-sexworker women attending STD clinics in Pune, India. In addition, 400 HIV-discordant couples will be enrolled. Thus, a total of 800 HIVuninfected and 400 HIV-infected participants will be enrolled.

Patients attending three established outpatient STD clinics in Pune, India will be recruited into this prospective cohort study. In addition, NARI has a HIV Reference Clinic facility on the premises of National Institute of Virology, Pune. This site will also provide a referral base for recruiting HIV discordant couples. In addition, we have also successfully negotiated a clinic space in Talera Hospital in Chinchwad, an adjoining Municipal hospital and we are hoping to initiate a HIV reference clinic to this center that could screen and enroll high-risk women and HIV discordant couples.

There are two basic risk groups to be recruited into this cohort study, reflecting our goal to specifically prepare for initiation of the HPTN 035 and 052 trials. The two groups in this cohort study will be

A) High-risk women, who are not commercial sex workers. These include women presenting to the STD clinics and referred women who are the spouses of the male STD patients. (Male STD patients are encouraged to refer their partners/wives to the clinic for evaluation and treatment of STDs and HIV screening).

B) HIV discordant couples. These will be expected to be primarily HIV-infected men identified at screening and their HIV-uninfected wives. We do not expect to identify very many HIV-discordant couples where the woman is the HIV-infected index case and the man is HIV-uninfected. However, such discordant couples would also be eligible for enrollment. As outlined below (Section 3.3), discordant couples will be enrolled following a three-step procedure (index partner, exposed partner and discordant couples) that involves inclusion criteria and informed consent at each step. Also, it is understood that index partners may have more than one sexual partner. This protocol only requires participation of one such regular partner. The index partner will be enrolled in the study.

Following initial HIV screening, 400 HIV-uninfected women and 400 HIV-discordant couples (total n=1200) will be offered enrollment in this study based upon the following eligibility criteria.

3.2 Inclusion Criteria HIV-uninfected Women (n=400)

HIV-uninfected individuals attending the STD clinics (n=400) must meet all of the following criteria in order to be eligible for inclusion in this cohort study:

- Age 18 and older
- Able and willing to provide written informed consent for HIV testing and to take part in the study.
- HIV seronegative by licensed ELISA.*
- Available for at least 12 months of study follow-up.
- Must agree to receive their HIV test results.

*Note: Individuals with only a single ELISA test positive, i.e. with a negative confirmatory ELISA will be considered HIV seronegative and eligible for enrollment.

3.3 Inclusion Criteria HIV-discordant Couples (n=400 couples)

3.3.1. HIV-infected partners (index partner) of HIV-uninfected patients attending the STD clinics must meet all of the following criteria in order to be eligible for inclusion in the cohort study:

- Age 18 and older
- Able and willing to provide written informed consent for HIV testing and to take part in the study.
- HIV seropositive by 2 different licensed ELISAs
- Willing to receive their HIV test results.
- Available for at least 12 months of study follow-up
- Presently in a sexual relationship with the same partner for at least three months duration
- Intend to remain with this partner for the duration of the study
- Willing to identify his/her sexual partner and disclose his/her HIV status to partner.
- Willing to attempt to recruit their partner

3.3.2. Partners of HIV-infected index partners who meet eligibility criteria 3.3.1. above must meet all of the following criteria in order to be eligible for HIV screening:

- Age 18 and older
- Able and willing to provide written informed consent for HIV testing
- HIV seronegative by licensed ELISA
- Willing to receive their HIV test results.

3.3.3. HIV-discordant couples who meet initial criteria 3.3.1 and 3.3.2 above must also meet all of the following criteria in order to be eligible for inclusion in the cohort study:

- Each partner agrees to participate in the study together
- Each partner is able and willing to provide written informed consent to take part in the study.
- The partners have been in a sexual relationship for at least the prior 3 months.
- Each partner is available for at least 12 months of study follow-up
- Each couple has stated intention to continue their relationship for the duration of the study (12 months).
- Each partner is willing and able to attend each scheduled follow-up study visit

3.4 Exclusion Criteria

Persons who meet any of the following criteria will be excluded from the studies:

- HIV-uninfected women who report a history of prior commercial sex work will not be eligible for enrollment either as part of the female cohort or as an HIV-uninfected partner of an HIV-infected man. However, HIVinfected female commercial sex workers can be enrolled in the HIVdiscordant partners study with their HIV-uninfected male primary sexual partner
- Have an obvious psychological/psychiatric disorder that would preclude provision of informed consent or otherwise contraindicate study participation.
- Have any other condition that, in the opinion of the investigator, would preclude provision of informed consent, make participation in the study unsafe, complicate interpretation of study outcome data, or otherwise interfere with achieving the study objectives.
- Discordant couples who report a history of domestic violence will be excluded from the study.*

*Because the women's interview will raise issues of physical, sexual, or psychological abuse, the interviewers will be trained to discuss these emotionally charged issues, and will be able to refer women for help. Agencies in Pune will be identified as referral resources. A psychologist with experience counseling victims of domestic violence will be hired as a training consultant. Maintaining the privacy of counseling interviews and research interviews is essential to protect the respondents from incurring abuse as a result of responding to these questions. Their husbands will not be asked any questions about domestic violence, nor will they be told if their wife does report a history of violence and the couple is disqualified from the study. Thus, we will follow current WHO ethical and safety recommendations for research on domestic violence against women (www.who.int/violence_injury_prevention/vaw/ethicsenglish.htm) The counselors will de-brief the women at the end of the survey, giving them ready responses for husbands or other family members who inquire about the nature of the questions.

3.5 Withdrawal

Once a participant has enrolled in the cohort study, we will make every reasonable effort to retain him/her for at least 12 months of follow-up. Retention rates of at least 95% are targeted for this observational cohort study. However, participants will have a right to withdraw from the study for any reason at any time if they so desire. The investigator also may withdraw participants from the study in order to protect their safety and/or if they are unwilling or unable to comply with required study procedures. Participants also may be withdrawn if the sponsor or regulatory authorities terminate the study prior to its planned end date.

4 STUDY PROCEDURES

The objective of our efforts will be to ensure the availability of a sufficiently large cohort of high-risk men and women for participation in the multiple HPTN clinical trials, with incident HIV infection as the primary outcome measure. Our goal will be to continue to screen 2000 new male and female high-risk patients/year, with an expected HIV prevalence of 20%. Of the 1600 HIV-uninfected individuals, we will anticipate enrollment of approximately 400 new non-sex worker women over the first 12 months into this follow-up study of HIV seroconversion. We will also enroll 400 HIV-discordant couples. The estimated study time line is outlined in the chart below.

		HPTN 034 Initiation ▼				
Sept	March	Sept	March	Sept	March	Sept
2000	2001	2001	2002	2002	2003	2003
I	I	I	I	I	I	I

HPTN 034 Timeline

HPTN 034 Screening/Enrollment (n=1200 enrolled, 400 HIV- women +400 HIV discordant couples) I------I HPTN 034 Follow-up

4.1 Screening

We will continue to inform all new STD patients that we are offering a free, voluntary HIV test and we will examine and treat the patient for an STD or other infections or medical problems (See Section 4.6 below). For this study, our standard syndromic STD diagnosis and treatment procedures (for screening and follow-up) will be followed.

Men and women with symptoms and/or signs of a genital ulcer disease will be offered one of the following 4 syndromic treatment options by the clinicians:

A: Inj. Ceftriaxine 250 mg IM and Cap. Doxycycline 100 mg BID*14

OR

B: Inj. Ceftriaxone 250 mg IM and Tab Azithromycin 1 gm stat

OR

C: Cap Doxycycline 100 mg BID*14 and Tab Ciprofloxacin 500 mg BID*3

OR

D: Tab Erythromycin 500 mg QID*15 [Pregnant women]

Men and women with symptoms and/or signs of genital discharge or urethritis/ cercicitis/ vaginitis will be offered one of the following 2 syndromic treatment options by the clinicians:

A: Inj. Ceftriaxone 125 mg IM and Cap Doxycycline 100 mg BID*14

OR

B: Ceftriaxone 125 mg IM and Tab Azithromycin 1 gm stat

AND

- 1 Tab Metronidazole 2 gm stat for Trichomonas
- 1 Tab Metronidazole 400 mg BID*7 OR Secnidazole 2 gm stat for bacterial vaginosis [BV]
- 2% Myconazole *7 OR Candid Vaginal Tablets V1 (1 day) or V6 (6 days) for vaginal candidiasis

If the patient refuses a HIV screening, we will treat the patient based on physical signs and symptoms, and invite them to come back any time for a free HIV test. If the patient agrees to have an HIV test, consent will be obtained, the patient will be examined by the doctor, blood will

be drawn and the patient will be asked to come back in approximately 7 days for the test results. Patients will also be offered free screening for syphilis. A short screening questionnaire will be administered to collect basic demographic and risk behavior data. As part of our pre-test counseling, all patients will be given a short oral presentation on the modes of acquiring HIV, correct use of condoms will be demonstrated using an anatomical model, and patients will be given as many condoms as they request.

4.2 Enrollment

When people return for their test results and post-test counseling (typically within 1 week of their screening visit), individuals will be informed that we are doing a study at the clinic and they will be invited to join the observational follow-up study. The requirements of this observational study (follow-up for 1 years, phlebotomy, physical exams and questionnaires) are designed to prepare the participants and project staff for HPTN 035 and 052 clinical trial protocols. Of the 800 HIV- uninfected participants targeted for enrollment, 400 will be enrolled with their HIV-infected sexual partners. These 400 HIV-discordant couples will be consented, enrolled and followed as couples, using identical data forms and procedures (Note exception: HIV-infected partners will not have repeat HIV testing) as for the 400 HIV-uninfected women in this study. The procedures for participation in the cohort study will be thoroughly explained to each patient and couple. We will also inform the participants that we are preparing for some studies of new methods for preventing HIV infection in the near future.

Enrollment and recruitment will be done only by clinic counselors and physicians, who will answer all questions posed by patients. If the patient refuses to join the study at that time, they will be told that they can still return any time for medical care or to join the study at a later point. In addition, we will collect information about the reasons for their refusal to participate in the cohort study. Informed consent will be obtained from eligible and willing participants for all HPTN studies.

4.3 Follow-up Visits

Follow-up visit will occur every 3 months for 1 year. At every follow-up visit, a short questionnaire will be administered to all participants to assess their continued understanding from previous visits about the nature, duration, benefits and risks of being in the study and to assure their voluntary participation in the study. Patients seen in follow-up will also have a physical examination, be evaluated and treated for STDs, receive additional counseling and offered re-testing for HIV infection as outlined below. In addition, participants will also be invited to participate in additional assessments issues addressing retention using a series of focus groups, key informant interviews and individual qualitative and quantitative assessments. At each follow-up visit, we will also utilize exit interviews, focus groups and semi-quantitative methods to assess the factors identified at screening that are associated with retention and/or loss to follow-up in these newly enrolled individuals.

4.4 Detection of HIV infection

For this HPTU protocol, identification of incident cases of HIV-1 infection will be primary outcome measure. Sera will be initially screened with the Genetic Systems combination ELISA kit for detection of HIV-1 and HIV-2, which is our current ELISA screening method. Specimens that are positive by Genetic Systems ELISA will be confirmed for HIV-1 or HIV-2 infection by re-testing with a different ELISA (UBI HIV 1/2 EIA, United Biomedical, USA). All HIV testing will be performed on site in Pune. The HPTN Central Lab will implement and monitor the quality control procedures for all of the laboratory assays for this protocol.

4.5 Interim Contacts and Visits

Interim contacts and visits may be conducted at participant request at any time during the study. Interim HIV counseling and testing will be provided as needed in response to participant reports of potential exposure to HIV. All interim contacts and visits will be documented in participants study records and on applicable case report forms.

4.6 Clinical Care for Study Participants

For this protocol we will continue our current standard of clinical care, which is to provide free diagnosis and treatment of all STDs, HIV VCT, as well as referral to the NARI TB clinic, the NARI HIV Clinic or to the many specialty clinics attached to Sassoon Hospital, if necessary. This clinical care package is offered to all walk-in patients in our clinics, whether or not they are enrolled in research studies. In addition the standard of clinical care for all patients attending the NARI clinics exceeds what is locally available to most patients with and without HIV infection. All outpatient clinical care costs, including the cost of most medications for STDs, opportunistic infections, TB and other common illnesses will continue to be provided free of charge to all participants. Specific clinical diagnostic testing and treatment to be provided to study participants and to those screened for possible study participation are outlined in detail in Section 4.1 above and 4.7. below.

Currently, anti-retroviral therapy is affordable to less than 5% of the HIV-infected patients in India. The cost of these medications has recently been significantly reduced by some companies in India (e.g. CIPLA). Despite these reductions, the medications will still cost an estimated \$600-\$1000/person per year, which is more than the yearly income of most of the HIV-infected individuals coming to the NARI clinics for HIV screening and STD treatment. In addition, there have been no clinical trials in India to measure the clinical efficacy of HAART. The impact of HAART for prevention of the most common causes of morbidity and mortality in India (TB, herpes zoster, neurological disease, bacterial pneumonia, diarrhea, etc) has not been measured or compared with the impact of other interventions, such as INH prophylaxis, cotrimoxazole prophylaxis and provision of adequate nutrition and clean drinking water. It is also unclear if the current North American guidelines for initiation of HAART (CD4<350) are optimal for Indian patients who are at great risk of HIV-associated death from diseases that occur at higher CD4 counts. A HPTN network wide policy is required for all protocols to define what should be the minimal level of care provided to all HPTN participants. In the absence of a policy and/or HPTN support for provision of HAART to all participants, we will continue to provide care that

is consistent with Indian government guidelines (National AIDS Control Organization and Indian Council of Medical Research). The Indian government currently does not require provision of HAART to HIV-infected participants in clinical trials.

HIV-infected participating in this cohort study, either index partners of a discordant couple or as a participant in the laboratory substudy (HPTN 034A) of recently infected persons will be offered the following additional care for the duration of this study (Section 4.6.1 and 4.6.2). HIV-infected individuals found at screening or seroconverters unwilling to participate in the 034A lab substudy will be offered referral to the NARI HIV clinic or to a local provider for clinical care.

4.6.1. All HIV-infected Enrolled Study Participants

- CBC and CD4 count every 3 months (Note: subjects enrolled in 034A substudy will follow schedule outlined in appendix for CD4 monitoring)
- HIV viral load every 6 months (Note: subjects enrolled in 034A substudy will follow schedule outlined in appendix for viral load monitoring)

4.6.2. Symptomatic (or CD4<200) HIV-infected Enrolled Study Participants

• Cotrimoxazole prophylaxis (Based on UNAIDS guidelines for sub-Saharan Africa)

4.6.3. HIV-infected Persons identified at Screening or HIV seroconverters not participating in the HPTN 034A Laboratory Sub-study

- Referral to Indian Government supported NARI HIV clinic: This clinic provides free counseling CD4 counts every 6 months, yearly viral load, co-trimoxazole prophylaxis, multivitamins, medical care for specific illnesses as per the national standards of care and referrals to specialty care at the local government hospital, when required.
- Patients will also be offered option of referral to local physicians experienced in the care of HIV-infected individuals.

4.7 Ancillary HPTN Core Laboratory Studies

Participants in this 034 protocol may also be eligible to enroll into one of two proposed ancillary laboratory sub-studies (Acute HIV Study 034A and Exposed-Uninfected Study 034B), directed by the HPTN Core Laboratory. Details of these sub-studies are included in the appendix. In addition, to prepare the site for upcoming trials and to establish required QC for microbiological assays that will be required, some additional laboratory tests to diagnose the etiology of STDs will be undertaken in symptomatic STD screened and enrolled subjects. Although, as mentioned above, treatment of screened and followed patients will follow a syndromic algorithm, the following additional STD laboratory assays will be performed when clinically indicated:

4.7.1. STD Diagnostic Procedures Offered to All Women Presenting to the STD Clinics

All women presenting to the STD clinics in Pune will be routinely offered a pelvic examination that includes bimanual examination for adnexal masses or tenderness and speculum examination of vagina and cervix. The following STD diagnostic algorithm will be followed:

- **IF** abnormal vaginal discharge or purulent cervicitis is noted:
 - Collect specimen for wet mount for candida, trichomoniasis, and BV (pH and Gram stain).
 - Collect swab for *N. gonorrhoeae* and *C. trachomatis*
- **IF** ulcerative lesions are noted:
 - Collect swab for syphilis dark field microscopy and collect blood for syphilis serology.

4.7.2 STD Diagnostic Procedures Offered to All Men Presenting to the STD Clinics

All men presenting to the STD clinics in Pune will be routinely offered a physical examination which includes a genital examination. The following algorithm will be followed:

- **IF** genital discharge by report or examination is noted:
 - > Collect specimen for wet mount for candida, trichomoniasis.
 - Collect swab for *N. gonorrhoeae* and *C. trachomatis*
- **IF** ulcerative lesions are reported or examination is noted:
 - Collect swab for syphilis dark field microscopy and collect blood for syphilis serology.

4.7.3. Additional Protocol Specific STD Laboratory Procedures

Details of the STD laboratory Protocol specific procedures are pending from the HPTN STD Core Laboratory ([name], Director). Some additional laboratory procedures may be utilized in this protocol for participants in the cohort study, in anticipation of what will be required for the 035 and 052 protocols. The purpose of introducing these assays in this protocol will be to assist in the establishment of QC procedures with the HPTN STC Core Laboratory. These additional laboratory assays will be phased in to reflect final decisions about what assays will actually be utilized for the 035 and 052 trials. These may include:

- Examine InPouch culture for *T. vaginalis*.
- Conduct PCR for *N. gonorrhoeae* and *C. trachomatis*.
- Serology for HSV-2

4.8 Assessment of Barriers to Trial Participation and Retention

To prepare for upcoming HPTN trials, we need to explore attitudes and experiences regarding participation in clinical trials. We must thoroughly understand acceptance of HIV prevention research and willingness to participate in research and research trials. The constructs of 'clinical trials', 'randomization', 'placebo' etc. will need to be understood by potential research subjects. Exploring the cultural differences between researchers and potential subjects regarding these constructs will provide new information, enlighten research design and inform foundational ethical principles for upcoming trials. We will need to understand the local terms or concepts that capture these constructs so they can be incorporated into recruitment and informed consent strategies for HPTN trials. We will explore the kinds of information needed by potential study subjects and how they would like that information presented (flip charts, videos, verbal, written) and by whom (peer counselors, nurses, doctors). Lastly, we will explore people's reaction to the idea of biomedical research itself. We will conduct qualitative in-depth and focus groups methods to explore these kinds of questions like: Is it right for a doctor to try a new or untested therapy on a patient in order to see what happens? How is knowledge acquired in medical systems in India, i.e. Ayurvedic, allopathic or other? Who should benefit from research, participants, society or both? Who would you talk to, in order to decide to be in a research study? Why? What ways do you usually get new information? How do you prefer to get information on new problems, issues, or products? How do you usually make a decision about how to solve a problem? What is 'research'; how would you describe 'informed consent'? What local terms would be appropriate? Why would you enroll in a research study? Why not? What kinds of incentives would be appropriate for people to enroll in a study?

The qualitative research plan consists of a triangulation of ethnography, focus group discussions, and indepth interviews of potential participants. Focus group guides have been developed for HIVNET 013, and will be used as the basis for FGD by trained facilitators. These guides are standardized, and outline the specific topic areas for data collection and elaboration. In addition, standardized guides will be developed for in depth interviews. Transcripts from FGD and indepth interviews will be reviewed for completeness, entered into a database verbatim, reviewed for topical areas and coded in the local language, and analyzed. Informants for in-depth interviews and focus group discussions will be purposively sampled based on the following criteria: HIV-negative, native Marathi or Hindi speaker, currently involved in research at the clinic or recently experienced the research process at the clinic and are thus knowledgeable about the topic of interest, able and willing to discuss issues related to research participation and procedures.

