4.8.1. Qualitative interviews

At the enrollment visit, a subset of 15-18 HIV negative eligible women and 20-25 eligible couples will be purposively selected and invited for in-depth qualitative interviews (Eligibility is defined as those who meet the criteria for enrollment as described in section 3.3 of the protocol). Half of the sample of in-depth respondents will be obtained from those who refuse to enroll in the study, to assess their concerns about study participation and their understanding and opinions about research and clinical trials.

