Qualitative data analysis: In addition, corresponding to secondary study objectives, the HIV risk behaviors and assessment of barriers to enrollment and retention of study participants, in both the cohort and the community study will be described. In order to prepare for possible participation in the HPTN 052 trial, we will utilize qualitative and quantitative social science techniques to identify and address particular behavioral and social barriers to enrollment and retention of HIV discordant couples. In addition, the rate

of participant retention for each study follow-up interval, and across all four study visits, will be calculated. The baseline demographics and HIV risk behaviors of women and couples completing and not completing scheduled follow-up will be compared.

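### Section 4.8 limits interview and focus-group informants to HIV-negative people, which contradicts the sampling of discordant couples in 4.8.1 and 4.8.2 and would shut out every HIV-infected index partner

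*Supplement*

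**What the plan says.** Section 4.8 gives a single criteria list for informants in both in-depth interviews and focus group discussions. They "will be purposively sampled based on the following criteria: HIV-negative, native Marathi or Hindi speaker, currently involved in research at the clinic", and the research-experience item continues with an alternative: "or recently experienced the research process at the clinic and are thus knowledgeable about the topic of interest".

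Section 4.8.1 sets the interview sample: "a subset of 15-18 HIV negative eligible women and 20-25 eligible couples will be purposively selected and invited for in-depth qualitative interviews". On who counts as eligible it says: "Eligibility is defined as those who meet the criteria for enrollment as described in section 3.3 of the protocol". Section 3.3 holds the discordant-couple criteria, and 3.3.1 requires the index partner to be "HIV seropositive by 2 different licensed ELISAs". Section 4.8.1 adds: "Half of the sample of in-depth respondents will be obtained from those who refuse to enroll in the study".

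Section 4.8.2 plans 4-6 focus groups of 6-8 people, drawn from eligible women and couples. Section 4.8.3 compares themes by gender, among other factors. Section 6.4 discusses the risks of including discordant couples in interviews and group interviews, among them disagreement between partners interviewed jointly.

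The purpose is stated under Section 5.4. To prepare for HPTN 052, qualitative and quantitative social science methods are to "identify and address particular behavioral and social barriers to enrollment and retention of HIV discordant couples".

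The 2004 letter of amendment and the clarification memos do not list Section 4.8, so this wording is current.

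**The concern.** A discordant couple has one HIV-infected member by definition. A rule that every informant be HIV-negative cannot stand beside a rule that couples be interviewed, and the protocol does not say which section governs.

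The consequence depends on which one staff follow. If they follow 4.8, the infected partner is never heard in an interview or focus group. That partner is the entry point for couple enrolment: under 3.3.1 he or she must be willing to disclose HIV status and to try to recruit the other partner. Section 4.8.3 lists a husband or partner refusing permission among the types of barrier, yet an infected husband could not be asked about it. Section 5.2 assigns the main questions on barriers and motivation to these two methods, so the gap falls on the instruments chosen for that secondary objective.

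**Working it through.** There is no test, power or precision figure here to reproduce. The sample is purposive and qualitative. The check compares the sections and then counts heads.

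**1. The sections side by side**

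| Section | Rule | Can an HIV-infected index partner take part? |
|---|---|---|
| 4.8 | Interview and focus-group informants are HIV-negative | No |
| 4.8.1 with 3.3.1 | 20-25 couples eligible under 3.3; index partner seropositive | Yes |
| 4.8.2 | Focus groups from eligible women and couples | Yes |
| 4.8.3 with 3.1 | Themes compared by gender; couples expected to be mainly infected men with uninfected wives | Needed if men are to be represented |
| 6.4 | Joint interviews of discordant couples | Yes |

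Section 4.8 stands alone against the other provisions.

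**2. Head count for the interviews**

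Inputs from 4.8.1: w = 15 to 18 women, c = 20 to 25 couples. Assumption: both members of each couple are interviewed. Section 4.8.1 does not say so; the joint interviews in 6.4 point that way.

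Respondents = w + 2c; index partners excluded by 4.8 = c; remaining = w + c.

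| w | c | Respondents | Excluded | Remaining | Share excluded |
|---|---|---|---|---|---|
| 15 | 20 | 55 | 20 | 35 | 20/55 = 36% |
| 15 | 25 | 65 | 25 | 40 | 25/65 = 38% |
| 18 | 20 | 58 | 20 | 38 | 20/58 = 34% |
| 18 | 25 | 68 | 25 | 43 | 25/68 = 37% |

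So 20-25 of 55-68 respondents would go, about 34-38%, and the remaining 35-43 would all be HIV-negative.

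If instead one HIV-negative member speaks for each couple, the sample is w + c = 35 to 43 from the start. Nobody is then removed, but no index partner is interviewed either, and the joint interviews in 6.4 have no place.

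**3. Focus groups**

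4 × 6 = 24 to 6 × 8 = 48 people. How many would be index partners is not stated, so no share can be given. Under 4.8 the number would be zero.

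**4. Effect on the comparison by gender**

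Under 4.8 the only men left are HIV-uninfected male partners of infected women. Section 3.1 expects few such couples, and the other cohort consists entirely of women. The documents give no number, so the conclusion is only that few men would be available.

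**The case against.** The strongest reply is that this is a drafting slip. The specific provisions (4.8.1, 4.8.2, 4.8.3 and 6.4) all point to including both partners, and staff who follow them lose nobody. The point touches one secondary objective, no primary endpoint and no statistical figure. A percentage lost from a purposive sample also has no meaning for precision. All of this stands, and it limits the weight of the point. It does not remove the contradiction: the list in 4.8 is written as an operative selection rule, and nothing gives the later sections precedence.

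Two stronger readings are tempting and should be set aside.

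- *A reader might infer that 4.8 also bars the refusers whom 4.8.1 wants for half its interviews.* The documents do not support this. Current involvement in research is one of two alternatives; the other is recent experience of the research process. Interviewees are selected at the enrollment visit, by which time they have consented to screening, been examined and tested, returned for results and been invited to join. Someone who then declines can meet the second alternative. The term is undefined, which is at most an ambiguity. Section 4.8.2 does not mention refusers.
- *A reader might infer that index partners vanish from the barriers objective altogether.* They do not. The list in 4.8 covers in-depth interviews and focus groups only. Exit interviews and individual assessments at follow-up (4.3) and recorded reasons for refusal (4.2) carry no HIV-negative limit, and Section 5.4 compares women and couples who do and do not complete follow-up.

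Those other sources are only a partial substitute. The follow-up methods reach only people who enrolled, recorded refusal reasons are not in-depth data, and the completer comparison uses baseline demographics and risk behaviours rather than stated barriers.

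**Conclusion.** The point holds, confined to in-depth interviews and focus groups. The HIV-negative criterion in 4.8 is incompatible with the couple sampling in 4.8.1 and 4.8.2, and it conflicts with 6.4 and with the comparison by gender in 4.8.3. Applied literally it would exclude every HIV-infected index partner from both methods: 20-25 of 55-68 interview respondents if both partners are interviewed, and an unstated number of the 24-48 focus-group participants. Few men would be left.

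The conclusion rests on two conditions: that staff apply 4.8 as written and, for the count, that each partner is a separate respondent. The result would be a weaker assessment of barriers for HPTN 052, not the loss of that objective. Incidence, retention and sample-size calculations are untouched.

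**What to change.** In the criteria list of Section 4.8, replace the HIV-negative item with: *HIV-negative women, and both the HIV-infected and the HIV-uninfected partner of discordant couples*. This brings 4.8 into line with 4.8.1, 4.8.2, 4.8.3 and 6.4.

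The cost is one change of wording. The numbers of interviews and focus groups already planned do not change, and no analysis has to be recalculated.
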